9.6. Data Management

This study will use previously collected data that have been deidentified, processed, and cleaned. Prior to initiating the study programming, procedures were implemented to assess the quality of responses including, but not limited to, response ranges, consistency, and skip patterns. Data entry was completed instantaneously as the respondent answered the survey questions. Therefore, there are no paper surveys to house or destroy, and no manual data entry is required. The database that houses the questionnaire responses allows for direct exportation into statistical software. Identifying information about panel members will not be released other than a single panel identification number. Therefore, the working data files contain no identifying information, apart from the panel identification number. Specifically, the dataset does not include names, addresses, or any other information that can personally identify the respondents.

Quality checks were implemented on the dataset before it became final. These checks included Internet Protocol (IP) address checks (i.e., ensuring the respondent resided within the country stated and that a single IP address was not associated with multiple panel accounts), completion times (ensuring a respondent did not complete the survey in a timeframe that was too short, implying inattentiveness), illogical/inconsistent data responses, etc. At the discretion of the data management team, respondents who failed these checks were excluded from the final dataset.

The statistical software package that will be used for the study is R 4.3.1 (R Project for Statistical Computing).

9.7. Data Analysis

The average treatment effect of treated (ATT) will be measured to evaluate the effects of Rimegepant vs. triptan among current Rimegepant users.

Based on clinical relevance, we will prespecify a list of variables to adjust for the comparison.

Inverse probability of treatment weighting (IPTW) will be conducted to adjust for confounding by the covariates. The propensity score for each participant will be estimated by logistic regression and by including the prespecified list of variables to adjust for. Weights for ATT will be calculated for both exposed (Rimegepant users) and unexposed group (triptan users)¹⁶. Stabilized weights will be used to address extreme weight values.

To confirm that the IPTW procedure is successful, the weighted Rimegepant users and triptan users will be compared on the covariates using standardized mean difference (SMD) to ensure both groups are adequately balanced across all weighting criteria. While there is no definitive cut-off for identifying imbalance in IPTW, as a rule of thumb, a standardized mean difference (SMD) that is >0.10 is indicative of imbalance¹⁷. This threshold will be applied to determine the quality of the weighting.

Once the weighting is confirmed to be successful, bivariate analyses will be conducted to compare the weighted cohorts on treatment satisfaction, HCRU, QoL, migraine-specific

disability, and work productivity loss. Specifically, categorical variables will be analyzed using chi-square tests or Fisher's exact tests for small samples; continuous variables will be analyzed using 2-sample t-tests. Non-parametric tests may be considered for comparisons on skewed variables (e.g., HCRU) when the sample size is small (e.g., <30). For bivariate comparisons, p-values <0.05, 2-tailed, will be considered statistically significant. If there are covariates that are unbalanced after weighting (i.e., SMD >0.1), those covariates will be adjusted for in the regression analysis of outcomes. Generalized linear models will be fit depending on the distributions of outcomes.

As a sensitivity analysis, the aforementioned IPTW and bivariate comparisons will be replicated after restricting the Rimegepant user cohort to the subset of those presumed to be acute treatment users (<12 days using Rimegepant).

A sensitivity analysis will be conducted by incorporating NHWS sampling weights into the IPTW process. Sampling weights will be applied in the logistic regression to predict the propensity score, and the final weight will be the product of the propensity score weight and the sampling weight. Bivariate comparisons will then be replicated after using these newly derived weights for the participants.

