9.5. Study Size

Sample size estimates, based upon preliminary feasibility, are provided below, in Table 2. The sample size for this study is fixed by the number of patients in the NHWS database who meet the imposed criteria.

Table 2. Estimated Sample Sizes

Patient Cohorts	n
Overall NHWS sample	75,007
Diagnosed with migraine	8,439
Triptan users (oral route only, no OTC) without Rimegepant use	1,340
Rimegepant users without triptan use	144
Rimegepant users (acute only) without triptan use*	112

*For sensitivity analysis.

Abbreviations: NHWS: National Health and Wellness Survey; OTC: over the counter

A sample size of 1) 130 and 2) 100 in each group (1:1 allocation) will have 80% power to detect an effect size of at least 1) 0.35 standard deviation (SD) units (indicative of at least a “small-to-medium” effect) and 2) 0.4 SD units (indicative of a medium effect), respectively, using a 2-group t-test with a 5% 2-sided significance level. We will have a sample size much greater than 130 in one of our groups, resulting in higher statistical power compared to the 1:1 allocation mentioned above. A total sample size of 100 will have 80% power to detect an effect size from a chi-square distribution of at least 0.33 (indicative of at least a “small-to-medium” effect) using a chi-square test with a 5% 2-sided significance level and 3 degrees of freedom. There will be sufficient power to detect a “small-to-medium” effect of Rimegepant user vs. triptan use on the outcomes in the main analysis, and sufficient power to detect a medium effect in the sensitivity analysis with acute Rimegepant users only.

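### Stabilising ATT weights only rescales the triptan group by a constant, so it cannot address extreme weights, and the plan has no other limit, weight report or stated variance method

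*Combined protocol and SAP*

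**What the plan says.** Section 9.7 takes current Rimegepant users as the target population, estimates the propensity score by logistic regression, and states: "Weights for ATT will be calculated for both exposed (Rimegepant users) and unexposed group (triptan users"). On large weights it has one sentence: "Stabilized weights will be used to address extreme weight values". It gives no stabilisation formula. The only check on the weighting is the SMD with a threshold of 0.10. For covariates that remain above the threshold, "those covariates will be adjusted for in the regression analysis of outcomes".

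The weighted cohorts are then compared at the two-sided 5% level. The plan says "categorical variables will be analyzed using chi-square tests", with Fisher's exact test for small samples, and "continuous variables will be analyzed using 2-sample t-tests". It names no variance method. In the sensitivity analysis with survey weights, "the final weight will be the product of the propensity score weight and the sampling weight", again with no limit or summary.

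Section 9.5, Table 2, gives estimated counts: 1,340 for "Triptan users (oral route only, no OTC) without Rimegepant use", 144 Rimegepant users in the main analysis and 112 in the acute-only analysis.

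**The concern.** Stabilisation reduces the spread of weights in some settings, but not for a point-treatment ATT. There the numerator is the same for every triptan user, so the most heavily weighted person dominates as much after stabilisation as before. A report could state that extreme weights were dealt with when nothing had changed, and readers would have no effective sample size or maximum weight to judge by. The SMD check and the regression fallback deal with imbalance. A comparison can pass every SMD check while resting on a few triptan users.

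The constant does change the total triptan weight, from about 144 to about 1,340. A test that takes this total as information will give a different standard error and p-value, although the data and the weighted estimate are the same.

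**Working it through.** **1. The plan's own figures.** Section 9.5 reproduces. A t-test with 130 per group at 0.35 SD has 80.3% power, and 100 per group at 0.4 SD has 80.4%. The calculation "using a chi-square test with a 5% 2-sided significance level and 3 degrees of freedom", with total N = 100 and effect size 0.33, gives 79.9%. These figures take no account of weighting, and the plan states no figure for the weights.

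**2. The constant.** Let p be the Rimegepant share. The stabilised triptan weight is [e/(1-e)] × [(1-p)/p], and (1-p)/p = n(triptan)/n(Rimegepant).
- Main: 1,340/144 = 9.31
- Acute-only: 1,340/112 = 11.96

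**3. What does not change.** Effective sample size is (Σw)²/Σw². Replacing w by kw multiplies top and bottom by k². The maximum/mean ratio and the weighted mean Σwy/Σw are unchanged for the same reason. As a numerical check, one simulated covariate was shifted by 0.5, 1.0 and 1.5 SD (144 v 1,340). Maximum/mean was 5.0, 14.8 and 62.5, and triptan effective n was 1,081, 526 and 142. All were identical before and after stabilisation.

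**4. What can change.** Nominal standard error of a mean difference, outcome SD 1:

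| Weights read as | Main, raw | Main, stabilised | Acute-only, raw | Acute-only, stabilised |
|---|---|---|---|---|
| Counts | √(2/144) = 0.118 | √(1/144 + 1/1,340) = 0.088 | 0.134 | 0.098 |
| Weighted least squares, model-based | √(288/1,482 × 2/144) = 0.052 | √(1,484/1,482 × (1/144 + 1/1,340)) = 0.088 | 0.053 | 0.098 |

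Stabilisation lowers one and raises the other. Both end at about the unweighted value, however uneven the weights are.

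Assumed weighted proportions of 40% v 30%, Pearson chi-square on weighted counts:
- Main: 3.17 (p = 0.075) raw, 6.08 (p = 0.014) stabilised
- Acute-only: 2.46 (p = 0.117) raw, 4.85 (p = 0.028) stabilised

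**5. Illustration under assumed separation.** The documents give no covariate distributions. Assumed: 42 propensity-model terms, ten shifted by the amount shown, outcome unrelated to covariates, stabilised weights, 1,500 runs per shift (Monte Carlo SE about 0.6 points at 5%, 1.2 at 30%). The last four columns are false-positive rates at nominal 5%. The chi-square tests have four levels.

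| Shift (AUC) | Triptan effective n | Max/mean weight | Robust SE | Means, model-based | Chi-square on counts | Means, sandwich | Rao-Scott |
|---|---|---|---|---|---|---|---|
| 0 (0.50) | 965 | 6 | 0.089 | 5.8% | 5.1% | 5.7% | 4.7% |
| 0.2 (0.67) | 652 | 12 | 0.092 | 7.2% | 6.9% | 5.9% | 5.3% |
| 0.3 (0.75) | 413 | 23 | 0.097 | 8.6% | 10.4% | 5.3% | 5.7% |
| 0.4 (0.81) | 227 | 44 | 0.108 | 13.3% | 18.0% | 6.1% | 6.1% |
| 0.5 (0.87) | 120 | 80 | 0.126 | 18.3% | 32.4% | 4.5% | 7.5% |

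With 30 of the 42 terms binary, the rates across the five shifts were 4, 5, 7, 8, 15% for means (model-based) and 7, 7, 9, 13, 25% for the chi-square on counts. With covariates explaining 30% of outcome variance, the model-based mean comparison gave 2, 3, 3, 7, 16% and the sandwich 2 to 4%.

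**6. Covariate-adjusted models.** Rescaling one group changes the pooled covariate slopes, so the adjusted estimate moves even with sandwich standard errors. At shift 0.5, with an outcome assumed to depend on the shifted covariates (300 runs), it moved by 0.027 SD on average (maximum 0.124), and significance flipped in about 5% of runs. A second check gave 0.026, 0.10 and about 3%. At shift 0.3 the movement was 0.004 SD with no flips.

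**7. Detectable effect.** At 80% power, 2.8016 × √(1/144 + 1/120) = 0.346 SD in the main analysis. Acute-only, with effective n 119: 2.8016 × √(1/112 + 1/119) = 0.369 SD.

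**The case against.** The strongest reply is that the false-positive rates come from an unstated variance estimator and not from stabilisation. Section 9.7 does not say that its tests are naive, and design-based chi-square and t-tests in R would fit its wording. This stands: the consequence for p-values is conditional.

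Stabilisation can also help. Under model-based weighted least squares, the unstabilised false-positive rates in the same simulation were 25.7 to 43.0%, against 5.8 to 18.3% stabilised. The constant also has a rationale, since it restores the triptan total to the group size. That total is still not the effective sample size.

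The table's null is favourable to the concern, because Table 1 labels every adjusted variable a potential confounder. When covariates predict the outcome, inflation of the mean comparison appears only under strong separation.

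A reader might infer that the planned p-values are wrong, or that the study loses its power. The documents support neither. The variance method and the real separation are unknown, and even an effective n of about 120 leaves detectable effects within the 0.35 and 0.4 SD of section 9.5. A reader might also infer that sandwich standard errors remove all dependence on scale. That is true only of unadjusted contrasts (step 6). Finally, the absence of a weight summary is a reading of the plan's silence.

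None of this restores the sentence on stabilisation. Normalising weights to mean 1 within a group is also only a rescaling.

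**Conclusion.** The concern holds in this form. Under the plan's own estimand, marginal stabilisation does not have the property that section 9.7 credits it with, and nothing else there limits or reports the weights. That part is algebra. The values 9.31 and 11.96 assume the marginal form of stabilisation and the estimated Table 2 counts, so they will follow the final counts.

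The effect on inference is conditional. If tests read weights as counts or use model-based variance, p-values depend on the constant and ignore uneven weights. The harm is small under mild separation and material under strong separation, and the documents do not show which applies. The simulated rates are illustrations only. In the strongest case Rao-Scott was itself somewhat above nominal, at 7.5% stabilised and 6.5% raw. This should be corrected before analysis, but it does not invalidate the design.

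**What to change.** Replace the stabilisation sentence with text that does the following:
- State the ATT weights and fix one scale for all analyses, for example unstabilised: 1 for Rimegepant users and e/(1-e) for triptan users. Claim scale-invariance only for unadjusted contrasts.
- Use sandwich or survey-design standard errors for means and generalized linear models, and a design-based test (robust Wald or Rao-Scott) for categorical outcomes, in place of plain weighted t, chi-square and Fisher tests.
- Report sparse or empty-cell tables descriptively, or collapse categories by a rule stated in advance. This matters for seven-level satisfaction in rarely used drug classes, which the four-level simulation did not test.
- Report triptan effective sample size, maximum weight and maximum/mean ratio for the main, acute-only and sampling-weight analyses. In the last, report them for the product weight and for both groups.
- Add one sensitivity analysis with triptan weights truncated at a percentile stated in advance. Untruncated weights stay primary.

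The cost is about one paragraph of protocol text and different R functions; no new data are needed and the covariate list can stay. Standard errors widen where weights are uneven (in the illustration, from 0.088 to 0.097 at shift 0.3 and 0.126 at 0.5). Sandwich errors are somewhat conservative when covariates predict the outcome (2 to 4% false positives in the 30% case). Truncation moves away from the exact ATT in a way that SMDs may not reveal, which is why it should remain a sensitivity analysis.

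### Section 9.7 names t, chi-square and Fisher's exact tests for ATT-weighted cohorts but no variance for unequal, estimated weights, so the 5% level is not assured in either direction

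*Combined protocol and SAP*

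**What the plan says.** Section 9.7 targets the average treatment effect in the treated (ATT). The propensity score comes from a logistic regression, and ATT weights are formed for both groups. On scaling it says only "Stabilized weights will be used to address extreme weight values", without a formula.

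Once balance is accepted, "bivariate analyses will be conducted to compare the weighted cohorts on treatment satisfaction, HCRU, QoL", migraine disability and work productivity. The named methods are:

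- Continuous outcomes: "continuous variables will be analyzed using 2-sample t-tests".
- Categorical outcomes: chi-square, or Fisher's "exact tests for small samples".
- Skewed outcomes in small samples: possibly non-parametric tests.
- Decision rule: "p-values <0.05, 2-tailed, will be considered statistically significant".

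For covariates whose standardized mean difference (SMD) stays above 0.1, "those covariates will be adjusted for in the regression analysis of outcomes". A sentence on generalized linear models follows. It does not say whether those models are weighted or how their standard errors are obtained.

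The tests are repeated in acute rimegepant users, and again with NHWS sampling weights, where "the final weight will be the product of the propensity score weight and the sampling weight" and "Bivariate comparisons will then be replicated after using these newly derived weights for the participants". Sections 9.6 and 9.8 name R 4.3.1 but no weighted routine. Annex 1 lists no standalone document.

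**The concern.** An ordinary t-test or chi-square test takes its standard error from the apparent number of patients. After ATT weighting this fails in two ways.

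1. **Unequal weights.** If the triptan weights sum to about 1,340, the test counts 1,340 full patients although the effective sample size (ESS) is smaller. This makes it too liberal.
2. **Estimated weights.** Fitting the score balances prognostic covariates in the sample and so reduces the variance of the difference. The ordinary test ignores this, which makes it too conservative.

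Scaling adds a third uncertainty. If the triptan weights instead sum to about 144, the test acts as if there were only 144 controls and is conservative.

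There is also a smaller problem: standard Fisher's exact test is not defined on non-integer weighted cells, and standard rank tests take no weights.

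These tests carry every outcome comparison, p<0.05 decides what is called significant, and section 8 says the findings may inform payers. With 144 exposed patients, or 112 in the acute analysis, a liberal test produces false differences and a conservative one hides real ones.

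**Working it through.** **Inputs from the documents.** Group sizes 144, 112 and 1,340 (Table 2); two-sided 5% and the tests above (section 9.7); propensity covariates (Table 1, section 9.3), counted as 42 model terms. **Assumed, because the documents do not give them:** weight distribution, covariate–outcome R², covariate prevalences and sampling-weight variation.

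**1. The plan's own power figures (section 9.5, unweighted) reproduce.** In the normal approximation, 130 per group at 0.35 SD gives Φ(0.35·√65 − 1.96) = Φ(0.862) = 80.6%, and 100 per group at 0.4 SD gives Φ(0.4·√50 − 1.96) = Φ(0.868) = 80.7%. For the chi-square, λ = 100 × 0.33² = 10.89 on 3 df gives 79.9%.

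**2. Analytic size when covariates explain none of the outcome.** ESS = (Σw)²/Σw² among triptan users. In SD² units the ordinary test uses V_ord = 1/144 + 1/Σw, while the variance is V = 1/144 + 1/ESS. The actual size is 2[1 − Φ(1.96·√(V_ord/V))].

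Weights scaled to sum to 1,340, so V_ord = 0.006944 + 0.000746 = 0.007691:

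| ESS | V | √(V_ord/V) | Size |
|---|---|---|---|
| 1,000 | 0.007944 | 0.984 | 5.4% |
| 400 | 0.009444 | 0.902 | 7.7% |
| 200 | 0.011944 | 0.802 | 11.6% |

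Weights summing to 144, so V_ord = 2/144 = 0.013889: the size is 0.8% at ESS 1,340 and 1.8% at ESS 400. Scaling by a constant leaves the ESS unchanged, so this difference comes only from the unstated formula.

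**3. Null simulation including estimation of the score.** 144 vs 1,340, 42 terms, 2,000 replicates per scenario (Monte Carlo SE about 0.5 points). Ordinary t-test, weights scaled to about 1,340:

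| Mean ESS | R² 0 | R² 0.1 | R² 0.3 | R² 0.5 |
|---|---|---|---|---|
| about 970 | 5.9% | 4.2% | 2.2% | 0.8% |
| about 716 | 6.2% | 5.3% | 1.8% | 1.0% |
| about 415 | 8.6% | 6.6% | 3.6% | 2.0% |
| about 262 | 12.6% | 9.6% | 5.9% | 5.8% |

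Of the 16 scenarios, 6 fall below 4%, 5 lie at 4–6% and 5 exceed 6%. The 12.6% exceeds the analytic 9.7% near that ESS; ESS varied widely between samples there (5th to 95th percentile 132 to 390).

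**4. Other tests and variances.**

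| Method | Null rejection |
|---|---|
| Ordinary t, weights summing to about 144 | 0–3.4% |
| Weighted-count chi-square, 1 df / 3 df | 2.1–12.2% / 3.6–17.2% |
| Fisher's exact on rounded weighted counts, 5% outcome, scaled / unscaled | 2.6–12.1% / 0.1–3.8% |
| Robust variance, weights held fixed | 0.6–6.0% |
| Stacked sandwich: t-type / 1 df / 3 df | 4.0–6.2% / 4.5–6.6% / 4.5–6.8% |

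- Acute analysis (112 vs 1,340): ordinary t 0.7–7.5%, stacked 4.5–5.3%.
- Product weights, assumed sampling-weight CV 0.3: ordinary t 0.9–10.2%, stacked 4.1–5.7%. At CV 0.6: 2.7–15.3% and 4.1–6.0%.

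**5. Other covariate structures.** A separate 22-covariate build (8 settings, R² 0 and 0.3) gave 1.7–10.0% for the scaled t-test, 0.3–3.1% unscaled and 4.2–5.9% with the propensity step in the variance. A 25-covariate build gave 0.2–8.4%, 0–2.1% and 3.9–7.1%. In that build the fixed-weight robust variance gave 0.1–7.4%.

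**The case against.** **The plan never says ordinary.** It compares weighted cohorts, and R can run weighted tests with suitable variances, so the analysts may do this correctly. That is possible, but the plan does not commit to it, and the second researcher who reviews the code (section 9.8) has no stated variance to check against. Annex 2 appears in the contents but not in the text available here, so the absence is established only for that text.

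**The generalized linear model sentence may apply generally.** It can be read that way, although it follows directly on the residual-imbalance rule. Under either reading, weighting and standard error remain unstated.

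**The sizes depend on invented covariates.** This stands. A rerun with a different 42-term mix (800 replicates) gave 4.2% where the grid shows 6.6%, and 9.6% at ESS about 320 where it shows 12.6%. Zero prognostic value is also hard to defend for MIDAS, WPAI or resource use, given adjustment for migraine days, headache days and comorbidity. In the grid no scenario with R² of 0.3 or more exceeds 5.9%, though the 22-covariate build reached 7.0% at R² 0.3. For such outcomes the conservative error deserves at least as much attention. Restricting to replicates that pass the SMD rule changed little.

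**A simple robust or survey-design variance would be a one-sentence fix.** It removes the liberal error from unequal weights but is conservative when covariates are prognostic: 1.6–2.9% at R² 0.3 in the 22-covariate build. It is a reasonable fallback.

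**Consequences are limited.** Section 9.9 disclaims causal inference, and power is little affected: 80% power with 144 exposed needs about 0.25 SD at ESS 1,000 and 0.29 SD at ESS 266, within the stated 0.35. The damage is to p-values and to any intervals.

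**Conclusion.** The concern holds, and the text should be corrected before analysis. Applied as written, the named tests do not deliver a 5% level, and the unstated scaling alone can move them from liberal to conservative. Confidence is high that the specification is missing and that error can go either way. The individual rejection rates illustrate a range under assumed ESS, R² and covariate structure; they do not predict this dataset. The net direction here is unknown and may differ between outcomes.

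**What to change.** Amend section 9.7 as follows.

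- Replace the ordinary tests on weighted cohorts with weighted outcome regressions suited to each outcome type, adding any covariate with SMD above 0.1.
- Take the variance from stacked estimating equations that include the propensity model, or from a bootstrap that refits it.
- State a rule for separation, for example that an indicator with no exposed patient leaves the propensity model in that sample or resample. With the 11 contraindication indicators at assumed prevalences of 1–5%, at least one had no exposed patient in 20–58% of simulated 144-patient samples, 54–70% of their resamples and 75% of 112-patient resamples.
- Name a fixed-weight robust or survey-design variance, with a design-based chi-square for categorical outcomes, as the fallback, noting that it can be conservative for ATT.
- Drop Fisher's exact and unweighted rank tests for weighted comparisons.
- State the stabilization formula.
- Carry the sampling weights through the same procedure in the second sensitivity analysis.
- Report ESS per group and 95% confidence intervals.

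The cost is wording, some programming and computing time, with no new data. Some p-values become less favourable: simulated power for 0.25 SD falls from 75.6% (from a test with a 12.6% null rate) to 66.6% at ESS 263 with R² 0. Others improve: 87.8% to 95.9% at ESS 716 with R² 0.5.

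Two limits remain. The bootstrap with the separation rule was tried in only four scenarios of 250 replicates (2.4–4.8%, Monte Carlo SE about 1.4 points). The rule covers single indicators only: up to 1.0% (144) and 1.5% (112) of replicates still had an unstable stacked standard error.

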8. RESEARCH QUESTION AND OBJECTIVES

The primary aim of this analysis is to assess PROs, specifically treatment satisfaction, HCRU, QoL, work productivity loss, and migraine-specific disability of Rimegepant users, relative to triptan users, among US adults diagnosed with migraine.

Secondarily, a sensitivity analysis will be conducted, applying a more restrictive definition for the Rimegepant user cohort, to corroborate the initial set of results. Findings from these analyses may be used to inform communications with payers regarding reimbursement of Rimegepant.

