9.3. Variables

The NHWS includes self-reported data on demographics, health characteristics, disease history, and health outcomes. The Table 1 below provides further details on the specific variables that will be assessed in the study.

Table 1. Study Variables

Variable	Role	Operational Definition
Rimegepant vs. triptan use	Exposure	Current Rimegepant users (for sensitivity analysis restricted to acute Rimegepant users with <12 days use per month) vs. triptan users (no OTC, oral route only).
Outcomes: Migraine treatment use and treatment satisfaction		
Migraine medication type (drug or OTC)	Outcome	Defined as drug only, OTC only and both drug and OTC, based on current use of migraine medication classes
Migraine treatment type (acute or prevention)	Outcome	Defined as acute only, prevention only and both acute and prevention, based on current use of migraine medication classes
Total number of acute migraine agent drug (continuous)	Outcome	Total number of acute agent classes (both drug and OTC) used
Total number of acute migraine agent drug (categorical)	Outcome	Including 1 drug class, 2 or more drug classes, and 3 or more drug classes based on the total number of acute agent (both drug and OTC) classes used
Total number of prevention migraine agent drug (continuous)	Outcome	Total number of prevention agent classes (only drug) used
Total number of prevention migraine agent drug (categorical)	Outcome	Including 1 drug class, 2 or more drug classes, and 3 or more drug classes based on the total number prevention agent classes (only drug) used
Current migraine treatments (drugs)	Outcome	Defined as yes or no for current migraine treatments on drug classes including: Rimegepant, triptans, NSAIDs, opioids, barbiturates, ergots, gepants (acute, including Rimegepant), ditans, combination analgesics, other acute drugs, anticonvulsants, beta-blocker, antidepressant, CGRP mAb, botox, and gepant (prevention, including Rimegepant)
Treatment satisfaction (drugs)	Outcome	Treatment satisfaction of drug classes of: Rimegepant, all acute agents, triptans, NSAIDs, opioids, barbiturates, ergots, gepants (acute), ditans, combination analgesics, other acute treatment, all prevention agents,

		anticonvulsants, beta-blockers, antidepressants, CGRPs mAb, botox, and gepant (prevention) Categorized into 7 categories: extremely dissatisfied, very dissatisfied, somewhat dissatisfied, neither dissatisfied nor satisfied, somewhat satisfied, very satisfied, extremely satisfied

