Current migraine treatments (OTC)	Outcome	Defined as yes or no for current migraine treatments on OTC classes of analgesics (acetaminophen only), analgesics (combinations), NSAIDs, other OTCs
Treatment satisfaction-analgesics (acetaminophen only)	Outcome	Treatment satisfaction of OTC classes of analgesics (acetaminophen only), analgesics (combinations), NSAIDs, and other OTCs Categorized into 7 categories: extremely dissatisfied, very dissatisfied, somewhat dissatisfied, neither dissatisfied nor satisfied, somewhat satisfied, very satisfied, extremely satisfied
Outcomes: HRQoL		
RAND-36	Outcome	PCS, MCS, and GCS index scores of the RAND-36 ¹²
EQ-5D-5L	Outcome	Health state utilities and the EuroQoL Visual Analog Scale (EQ-VAS) ¹³
WPAI-GH	Outcome	Absenteeism (% of work time missed because of one's health in the past 7 days), presenteeism (% impairment experienced while at work in the past 7 days because of one's health), overall work impairment (combination of absenteeism and presenteeism), and activity impairment (% impairment in daily activities because of one's health in the past 7 days) among total population, employed, unemployed, and disabled ¹⁴
MIDAS	Outcome	Total score, categorical (grade I-IV), and item scores (1-7) of MIDAS ¹⁵
Outcomes: HCRU		
ER visits	Outcome	Visited ER in past 6 months (yes or no); number of ER visits in past 6 months among total population and participants with ER visits
Hospitalizations	Outcome	Was hospitalized in past 6 months (yes or no); number of hospitalizations in past 6 months among total population and participants with hospitalizations
General practitioner/family practitioner visits	Outcome	Visited general practitioner/family practitioner in past 6 months (yes or no); number of general practitioner/family practitioner visits in past 6 months among total population and participants with general practitioner/family practitioner visits
Cardiologist visits	Outcome	Visited cardiologist in past 6 months (yes or no); number of cardiologist visits in past 6 months among total population and participants with cardiologist visits
Neurologist visits	Outcome	Visited neurologist in past 6 months (yes or no); number of neurologist visits in past 6 months among total population and participants with neurologist visits

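### About 56–61 comparisons in five unranked domains are each called significant at p<0.05, with no primary outcome or multiplicity control, so some chance findings are likely

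*Combined protocol and SAP*

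**What the plan says.** Section 8 gives five domains equal standing: "The primary aim of this analysis is to assess PROs, specifically treatment satisfaction, HCRU, QoL, work productivity loss, and migraine-specific disability of Rimegepant users". The comparator is the triptan cohort. In Section 9.3, every measure under the outcome headings of Table 1 has the same role, Outcome, and none is marked as primary or key.

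Many entries hold several comparisons. The MIDAS entry, for example, reads "Total score, categorical (grade I-IV), and item scores (1-7) of MIDAS". The prescription-drug satisfaction entry begins "Treatment satisfaction of drug classes of: Rimegepant, all acute agents, triptans, NSAIDs, opioids, barbiturates, ergots, gepants (acute), ditans, combination analgesics, other acute treatment" and continues through the preventive classes. A further entry covers "Treatment satisfaction of OTC classes of analgesics (acetaminophen only), analgesics (combinations), NSAIDs, and other OTCs".

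Section 9.7 says that, after weighting, "bivariate analyses will be conducted to compare the weighted cohorts on treatment satisfaction, HCRU, QoL, migraine-specific". The list then ends with disability (completing the last quoted term) and lost work productivity. The decision rule for bivariate comparisons follows: "p-values <0.05, 2-tailed, will be considered statistically significant". The comparisons are then repeated in two sensitivity analyses, one restricted to acute rimegepant users and one using the survey's sampling weights.

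Section 9.5 states power for a single test at a two-sided 5% level and concludes that power is sufficient for the outcomes. On use, Section 8 says: "Findings from these analyses may be used to inform communications with payers regarding reimbursement of Rimegepant". No section mentions multiplicity, a testing hierarchy or an exploratory status. Section 9.9, on limitations, is also silent on multiple testing.

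**The concern.** A 5% threshold limits the error rate of one test. When the same threshold is applied to several dozen tests and each result below it is called significant, some such results are expected even if the treatments do not differ. A reader then cannot tell which significant rows reflect a real difference.

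This matters because the plan claims both significance and sufficient power, and it foresees use with payers. Section 12 plans abstracts and posters, which have little room for dozens of rows. With no outcome named in advance, nothing in the protocol settles which rows carry the conclusion.

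**Working it through.** **1. The plan's own power figures (Section 9.5).** Normal approximation, two-sided 5%: power = Φ(d/√(2/n) − 1.960).
- d = 0.35, n = 130 per group: 80.6% (80.3% with the exact t).
- d = 0.40, n = 100 per group: 80.7% (80.4% with the exact t).
- Chi-square, N = 100, w = 0.33, 3 df, noncentrality 100 × 0.33² = 10.89: 79.9%.

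All three reproduce the stated 80%. Each is for one unadjusted test.

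**2. Number of comparisons in the five domains (Table 1).**

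| Domain | Count | Basis |
|---|---|---|
| Satisfaction | 22 | 18 drug classes or groupings + 4 OTC classes |
| Resource use | 18 | 6 visit types × 3 measures |
| Quality of life | 5 | RAND-36: 3 scores; EQ-5D-5L: utility and VAS |
| Work productivity | 4 or 7 | 4 WPAI scores; 7 if activity impairment is tested in 4 populations |
| MIDAS | 9 | total, grade, 7 items |
| Sum | 58 or 61 | |

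Section 9.2.2 excludes users of both drugs. Satisfaction with rimegepant and satisfaction with triptans therefore cannot each be compared between cohorts. Removing these two leaves 56 or 59, so the working range is 56–61.

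**3. Expected false positives if no true differences exist.** k × 0.05:
- 56 × 0.05 = 2.80
- 61 × 0.05 = 3.05

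This expectation does not depend on correlation between the tests. It does assume that each test has its nominal size.

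**4. Chance of at least one false positive.**
- Independent tests, 1 − 0.95^k: 94.3% for k = 56 and 95.6% for k = 61.
- Common correlation between test statistics (an assumption; the documents give none):

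| Correlation | k = 56 | k = 58 | k = 61 |
|---|---|---|---|
| 0.3 | 83% | 84% | 85% |
| 0.5 | 65% | 66% | 67% |
| 0.7 | 42% | 42% | 43% |

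**5. Cost of controlling five key outcomes.** The first Holm step uses 0.05/5 = 0.01. Detectable difference at 80% power = (2.576 + 0.842) × √(1/n₁ + 1/n₂), in SD units, with the unweighted sizes in Table 2:
- 144 vs 1,340: 0.300 SD (0.246 SD at 0.05).
- 112 vs 1,340: 0.336 SD (0.276 SD at 0.05).

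The plan's claims are 0.35 and 0.40 SD. ATT weighting reduces the effective triptan sample. Solving the same formula for n₂:
- 0.35 SD with 144 users: n₂ = 1/[(0.35/3.417)² − 1/144] ≈ 282.
- 0.40 SD with 112 users: n₂ = 1/[(0.40/3.417)² − 1/112] ≈ 210.

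For outcomes limited to employed respondents both groups shrink. If 60% are employed (an assumption), the detectable differences are 0.300/√0.6 = 0.387 SD and 0.336/√0.6 = 0.434 SD, both above the plan's figures. The 0.35 SD claim would need about 73% employed, since (0.300/0.35)² = 0.73, before any loss from weighting.

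**The case against.** The strongest reply is that this is a cross-sectional analysis of a fixed survey sample. Section 9.9 says causal inferences cannot be drawn, and a 0.05 rule for each comparison makes no familywise claim. That would carry weight if the plan called itself descriptive. It does not: it sets a significance rule, claims sufficient power and foresees use with payers.

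Other points stand and limit what can be said:
- **Near certainty.** A reader might infer that false findings are near certain. That needs independent tests, and these outcomes overlap heavily: MIDAS total, grade and items; three measures per visit type; RAND-36 with EQ-5D and WPAI.
- **A larger count.** Adding the 26 treatment-use rows of Table 1 to 58 or 61 gives 84 or 87. Those rows are labelled outcomes, but Section 9.7 does not list their domain for testing, so the documents do not clearly support that count.
- **Sparse classes.** Some satisfaction classes may have too few users to test, or may go to Fisher's exact test, which is conservative. About 3 is therefore nearer an upper figure than a central one.
- **Sensitivity analyses.** Section 8 describes the acute-user analysis as corroboration. Neither repeat should be counted as a new set of hypotheses.
- **Intent.** Section 8 says only that findings may be used with payers. The documents do not show that selective reporting is intended.
- **Cost of control.** The unweighted 0.300 and 0.336 SD do not by themselves show that control is cheap. They ignore weighting and the employed-only WPAI scores, and an SD-based figure does not describe a yes/no outcome or a seven-category one tested by chi-square.

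**Conclusion.** The point holds as a gap that should be closed. The plan applies an unadjusted 0.05 rule to about 56–61 comparisons in five unranked domains, with nothing that separates key outcomes from the rest. If no true differences exist, about 3 nominally significant results are expected in the main analysis. At least one has a probability of 94–96% under independence and about 84% or 65% at correlations of 0.3 or 0.5. Chance findings are likely, not near certain.

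The expected count rests on Table 1 and on tests of nominal size. The probabilities below 94% rest on assumed correlations. The documents support no conclusion about how results will be selected for publication.

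**What to change.** Revise Section 9.7 before analysis begins:
1. Name one key outcome per domain that can be compared between the cohorts. One possible set is MIDAS total score, EQ-5D utility, WPAI activity impairment in the total population, any ER visit, and satisfaction with all acute agents.
2. Test these five with Holm's procedure at an overall two-sided 0.05, and use the word significant only for them.
3. Report all other rows as estimates with 95% confidence intervals labelled descriptive, or with Benjamini-Hochberg adjusted p-values.
4. State that both sensitivity analyses corroborate the same five outcomes.

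The change takes a short passage of protocol text and one adjustment step in the code. Fewer rows will be nominally significant, and each key test loses some power. For continuous outcomes, the detectable difference at the first Holm step stays within the plan's 0.35 and 0.40 SD only while the effective triptan sample after weighting is at least about 282 (main analysis) and 210 (acute users). The effective sample size should be reported after weighting. Choosing activity impairment in the total population avoids the further loss that comes with employed-only scores.
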